4.4. Study Enrollment Procedures

Subjects will be recruited from 14 NeuroNEXT sites and 1 non-NN site in the United States. Investigators will be responsible for obtaining written consent from each potential subject after adequate explanation of the purpose, study procedures, and any risks associated with the study.

Treatment for each subject will be assigned by a randomized code. A block randomization scheme will be used to ensure approximately even distribution of subjects in treatment groups for each BMI strata.

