improvement in IENFD rather than just slowing of its rate of decline^{10,12,13}. Statistical power for the NQOL-DN was estimated based on an assumed SD for change in the NQOL-DN score over 2 years of 16.4 points, which conservatively allows for a 10% higher SD than the SD of 14.9 points reported for the change in the NQOL-DN in Boyd *et al*²⁴. If the correlation between baseline and follow-up assessments is ≤ 0.60 , 125 subjects with 12% loss to follow-up will provide 80% power with 2-sided $\alpha=0.05$ to detect a mean difference of 7.9 points between the treatment and control groups over 96 weeks after adjustment for the baseline NQOL-DN. This represents a difference of 4.0 points per year. This power calculation is conservative, as the multiple repeated QOL measurements in the study design will provide greater precision than the simplified ANCOVA based on a single follow-up time considered in this power calculation.

f. Decision for proceeding to a full-scale trial (“Go/No-Go” Algorithm). A full-scale trial will be justified if topiramate is demonstrated to be superior to placebo for either IENFD or NQOL-DN, and non-inferior for both of these outcomes. We estimated non-inferiority margins of up to 0.50 fibers/mm/year for the IENFD slope and up to an average of 5 points per year for the NQOL-DN. A failure to proceed to the full-scale trial would be problematic if there is a treatment benefit of 0.50 fibers/mm/year for the IENFD or of an average of 5.0 points per year for the NQOL-DN and the treatment does not have an adverse effect on the other outcome. Based on these conditions, the following global decision rule was developed: Proceed to the full scale trial if either:

1. The comparison of randomized groups favors topiramate by at least 0.30 fibers/mm/yr for IENFD and favors the placebo by no more than 2.70 points per year for the NQOL-DN, or
2. The comparison of randomized groups favors topiramate by at least 2.97 points per year for the NQOL-DN & favors the placebo by no more than 0.22 fibers/mm/yr for the IENFD.

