If the treatment does not affect NQOL-DN or another clinical endpoint, the M1 and M2 analyses will provide understanding of the null effect of the treatment. The evaluation of the profile of treatment effects in M1 will be performed by plotting the estimated treatment effects on each outcome with their 95% confidence intervals. Treatment effects on continuous and categorical variables will be estimated using linear or generalized linear mixed models analogous to those described in Aim 1; the treatment effect on the rate of falls will be analyzed using negative binomial regression. Concordant effects for IENFD and a particular clinical endpoint will suggest possible mediation of the treatment effect on the clinical endpoint through IENFD, whereas discordant effects will suggest IENFD did not play a major role (i.e. was not clinically relevant). Bootstrap resampling will be used to provide 95% confidence limits for ratios of treatment effects on IENFD vs. effects on the clinical endpoints.

The treatment effect estimates in the M1 analyses represent direct comparisons of randomized groups, and hence are not subject to confounding due to the randomized trial design. This is not the case for the M2 and M3 analyses, as confounding factors that jointly influence both the intermediate variables and the NQOL-DN or other clinical endpoints will lead to biased estimates⁸⁵. Failure to recognize this issue has led to confusion in prior applications of path analysis for evaluation of mediating factors⁸⁶. Thus, we will seek to identify and control for baseline and follow-up factors that may potentially influence both IENFD and NQOL-DN or other clinical endpoints in the M2 and M3 analyses.⁸⁷

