The regression coefficients of the IENFD slope in the M2 analyses will provide information concerning the clinical interpretation of the IENFD slope by characterizing the difference in the 96-week change in the NQOL-DN associated with a given difference in the IENFD slope. These analyses will be carried out using a joint mixed effects model in which the NQOL-DN will be assumed to be related to the underlying random IENFD slopes. We have experience fitting similar joint models using the SAS procedure NL MIXED⁸⁸. In the M3 analyses, the proportion of treatment effect explained (PTE) by the IENFD slope on the NQOL-DN will be obtained by first estimating the total effect of the treatment on change in the NQOL-DN to 96 weeks with adjustment for potential confounders but not the IENFD slope using a mixed effects model as

described in Aim 1, and then estimating the treatment effect on the change in the NQOL-DN that remains after controlling for the IENFD slope in a joint mixed effects model which adjusts for the IENFD slope in addition to the baseline confounders. The PTE by IENFD will be estimated by subtracting the ratio of the adjusted vs. unadjusted treatment effects from 1, and a 95% confidence interval constructed using bootstrap resampling. Similar analyses will be used to estimate the regression coefficients of the IENFD slope (for the M2 analyses) and the PTEs associated with IENFD (for the M3 analyses) for other clinical endpoints. To gain further insight into the effects of the topiramate intervention on different components of quality of life, the M2 and M3 analyses will be repeated for the five individual subscales of the NQOL-DN.

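### The M3 proportion explained and the M1 effect ratios divide by a treatment effect that lies about 2.8 SE from zero at the powered NQOL-DN difference, so the absolute mediated effect should lead

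*Combined protocol and SAP*

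**What the plan says.** Section 10 (Statistical Considerations), under the evaluation of the clinical meaning of IENFD change, treats this question as a major secondary objective and plans three analyses.

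- **M1** plots the treatment effect on each outcome with its 95% CI, and adds: "Bootstrap resampling will be used to provide 95% confidence limits for ratios of treatment effects on IENFD vs. effects on the clinical endpoints".
- **M2** estimates the regression of change in NQOL-DN and other endpoints on the IENFD slope, controlling for treatment.
- **M3** estimates the total treatment effect, then the effect after adjustment for the IENFD slope, and combines them: "The PTE by IENFD will be estimated by subtracting the ratio of the adjusted vs. unadjusted treatment effects from 1". The interval comes from bootstrap resampling. M3 is applied to NQOL-DN, to other clinical endpoints and to five NQOL-DN subscales.

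No precision is given for the proportion of treatment effect explained (PTE) or for the ratios, and no rule says when either should not be reported or interpreted. The text does say that M1 and M2 will be informative if treatment has no effect on an endpoint.

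Power is stated only for total effects. For NQOL-DN, "125 subjects with 12% loss to follow-up will provide 80% power" "to detect a mean difference of 7.9 points between the treatment and control groups over 96 weeks". For IENFD, the design has 80% power for 0.47 fibers/mm/year.

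**The concern.** A ratio behaves well only if its denominator is many standard errors from zero. A trial sized for 80% power puts the denominator, at the effect it is sized for, only 1.96 + 0.84 = 2.80 SE away. Some bootstrap resamples then have a denominator near or across zero, and the percentile limits can run far outside 0 to 1.

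M3 is the plan's only estimate of the size of the mediated effect. An interval that includes both no mediation and complete mediation would leave that question open, although the same two model fits also give a difference in points that does not have this defect. Neither a primary result nor the Go/No-Go decision is affected.

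**Working it through.** **Inputs.** From section 10, item e: 125 randomized with 12% loss, so 125 × 0.88 = 110 evaluable, or 55 per arm (equal allocation inferred from section 4.4: "A block randomization scheme will be used to ensure approximately even distribution of subjects in treatment groups for each BMI strata"); "an assumed SD for change in the NQOL-DN score over 2 years of 16.4 points"; baseline to follow-up correlation at its stated limit of 0.60; two-sided alpha 0.05; planned difference 7.9 points. From item f: a benefit of 5 points per year, and an IENFD/NQOL-DN correlation of −0.30.

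**1. The plan's own figure.**
- Raw SD = 16.4 / √(2 × (1 − 0.60)) = 18.34.
- ANCOVA residual SD = 18.34 × √(1 − 0.60²) = 14.67.
- SE of the difference = 14.67 × √(2/55) = 2.80 points.
- Detectable difference = 2.80 × 2.80 = 7.84, against the stated 7.9. Power at 7.9 is 0.806. The figure reproduces.

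**2. Distance of the NQOL-DN denominator from zero.**
- Powered effect: 7.9 / 2.80 = 2.82 SE.
- 5 points per year over 96/52 years: 9.23 / 2.80 = 3.30 SE. Taken as two years: 10 / 2.80 = 3.58 SE.
- If repeated measures cut the SE by 10, 20 or 30% (assumed range), 7.9 points lies at 3.1, 3.5 or 4.0 SE.

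An exact (Fieller) confidence set for the ratio is unbounded whenever the total effect is not significant. This happens in 19% of trials at 2.82 SE, 9% at 3.30 and 5% at 3.58.

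**3. Simulated bootstrap intervals.** 55 per arm, 600 trials, 600 stratified resamples, percentile intervals, linear model, IENFD slope treated as observed. In this model the true PTE = r × (IENFD effect in SE) / (NQOL-DN effect in SE), with r the size of the within-arm correlation. With both effects at 2.8 SE, the PTE equals r. The value r = 0.30 takes the size of the plan's correlation and applies it within arm; r = 0.50 is assumed.

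| Denominator | r | PTE intervals wider than 1 | PTE intervals containing 0 and 1 |
|---|---|---|---|
| 1.5 SE | 0.30 | 86% | 71% |
| 2.3 SE | 0.30 / 0.50 | 64% / 76% | 43% / 38% |
| 2.8 SE | 0.30 / 0.50 | 42% / 55% | 23% / 20% |
| 3.3 SE | 0.30 / 0.50 | 28% / 34% | 14% / 13% |
| 3.55 SE | 0.30 / 0.50 | 17% / 28% | 7% / 9% |
| 4.0 SE | 0.50 | 12% | 4% |

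The IENFD effect is 2.8 SE throughout, except 3.0 in the 3.55 row. At 2.8 SE the median PTE interval is 0.02 to 0.89 (r = 0.30) or 0.13 to 1.26 (r = 0.50). The M1 ratio, true standardized value 1.0, has median interval 0.19 to 2.66 or 0.30 to 2.35, and includes 0 in 35% or 28% of trials.

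**4. Where the bad intervals arise (2.8 SE).** Among trials with a significant total effect, only 3 to 6% of PTE intervals contain both 0 and 1. With about 80% of trials significant, these contribute 0.80 × 3 = 2.4 to 0.80 × 6 = 4.8 of the 20 to 23 percentage points. Width is less confined. Even if every non-significant trial (20%) is counted as wide, 42 − 20 = 22 to 55 − 20 = 35 points remain, which is 22/80 = 28% to 35/80 = 44% of the significant trials.

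**5. The alternative.** In the same set-up, the interval for total minus adjusted effect excludes zero in 72 to 83% of trials at 2.8 SE, against 56 to 70% for the PTE. With a denominator at 1.5 SE the figures are 73 to 78% against 23 to 33%.

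**The case against.** The strongest reply has four parts.

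1. *The denominator may be further from zero.* A reader might infer that 2.8 SE is the best the trial can offer. The documents do not support that. It is the value at the detectable difference, in a calculation the plan calls conservative: SD raised by 10%, one follow-up time although six are collected, correlation at its limit. At 5 points per year it is 3.3 to 3.6 SE. This stands. Nor can one say that other endpoints must be worse, since no effect or SD is given for them.

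2. *The plan has other summaries.* A reader might infer that ratios are its only evidence on mediation. They are not: the M2 coefficients and the M1 plot of separate effects do not divide by a treatment effect. This stands. It remains true that M3 names no absolute mediated effect, though it fits both models needed.

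3. *The worst intervals come from trials with no demonstrated effect to explain.* Largely true for intervals containing both 0 and 1. But the plan has no rule for that case, and many intervals stay wider than 1 among significant trials.

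4. *A proportion is what was asked for.* Section 1.2 asks for the relative contribution of IENFD change, which points alone do not answer. Moreover, showing the PTE only after a significant total effect selects inflated denominators: in simulation the median PTE fell from 0.29 to 0.27 and from 0.49 to 0.47. This is a good reason to keep the PTE and always show it.

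**Conclusion.** The point holds as a cheap improvement, not as an error in the plan. At the powered NQOL-DN effect, roughly half of the PTE intervals (42 to 55%) would span more than the whole possible range, and about one in five would contain both 0 and 1. At 3.3 to 3.55 SE these fall to 17 to 34% and 7 to 14%; by 4 SE the problem is small. For the subscales and other endpoints its size cannot be stated from the documents; 1.5 SE only illustrates a weak endpoint.

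The figures rest on a linear model with an observed IENFD slope, within-arm correlations of 0.30 to 0.50, and equal arms. The planned joint model with latent slopes may give wider or narrower intervals. The absolute effect is also no protection against the confounding that the plan already acknowledges for M2 and M3.

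**What to change.** Change the SAP wording for M3 and M1.

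- **M3, lead estimate:** the absolute indirect effect, defined as total minus IENFD-adjusted treatment effect in the endpoint's own units, with a bootstrap 95% CI from the resamples already planned. Apply it to NQOL-DN, the five subscales and the other clinical endpoints.
- **M3, PTE:** keep it as a descriptive secondary summary, always shown beside the total effect and its 95% CI, and not interpreted when that CI includes zero.
- **M1:** rely on the planned plot of separate effects with their CIs, on a standardized scale, and treat the ratios as descriptive under the same condition on the denominator.

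The cost is a few sentences. No new data, models or resampling are needed. The downside is that the lead result is no longer a single percentage.

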10.1. Outcomes

10.1.1. Primary Outcome (including definition)

IENFD and the validated NQOL-DN will serve as co-primary outcome measures. Rationale: The choice of endpoint measures is innovative, and validation of both measures as potential endpoints for use in a future Phase III trial is a major secondary objective of the current proposal. Most diabetic neuropathy trials use nerve conduction studies and clinical examination scales [e.g. the Neuropathy Impairment Scale Lower Limb (NIS-LL)] as primary outcome measures. However, these measures are unresponsive to change in early neuropathy⁶⁶ and their patient-based clinical meaning has not been established. Current criteria for the minimal clinically important difference in nerve conduction parameters are based on expert opinion from nearly 25 years ago⁶⁷. IENFD was selected as an objective measure of axonal integrity. NQOL-DN was chosen as a validated neuropathy specific measure of patient reported function and QOL.

The Norfolk Quality of Life – Diabetic Neuropathy (NQOL-DN) scale: IENFD provides an essential objective biomarker of axon structure but the patient focused clinical meaning of change in IENFD has yet to be conclusively determined. Therefore, incorporation of a validated measure of patient symptoms and function is necessary. Neuropathy clinical trials should assess the impact of therapy on patient function and QOL. Pain, sensory loss, imbalance, falls and reduced mobility combine to reduce QOL. The NQOL-DN captures the full spectrum of DPN related symptoms. Data from over 1000 structured clinical interviews was reviewed for content validity in an iterative multispecialty process in order to develop the instrument²⁷. 47 Items inventory DPN symptoms and their impact on function and activities of daily living. The NQOL-DN accurately distinguishes patients with and without DPN, and correlates significantly with other DPN measures²⁷. The NQOL-DN is responsive to change. In an 18-week double blind crossover trial of ruboxistaurin, topiramate and placebo, total NQOL-DN improved significantly with both topiramate (12.2+/-2.76) and ruboxistaurin (-9.6+/-4.1) but not placebo (-5.6+/- 3.5)²⁴. Topiramate reduces pain, and in a small clinical study was associated with increased IENFD over 18 weeks²⁵, suggesting an effect on small axons. By inhibiting protein kinases C-beta, Ruboxistaurin is thought to inhibit microvascular injury. Factor analysis has been used to group NQOL-DN items into 6 subscores: symptoms, autonomic, small fiber, large fiber, and activities of daily living. These different subdomains were differentially responsive to ruboxistaurin and topiramate. Topiramate treatment

was associated with a significant improvement in the small fiber and symptom subscores, which in turn significantly correlated with change in IENFD²⁴. By contrast, ruboxistaurin significantly improved only the large fiber subscore. These results suggest NQOL-DN subscores are physiologically valid measures that reflect different peripheral nerve populations. NQOL-DN will serve as the co-primary outcome measure.

Intraepidermal nerve fiber density: Both CSPN and early diabetic neuropathy frequently result in loss of small unmyelinated axons before loss of larger myelinated fibers. NCS evaluate myelinated axons, but are not affected by loss of small lightly myelinated or unmyelinated axons. While unmyelinated axons may be particularly vulnerable to metabolic stress, they are also more plastic than myelinated fibers, and have more robust regenerative capacity⁶⁸. Thus a validated biomarker of small fiber integrity would be a preferred endpoint in a CSPN clinical trial. IENFD directly reflects nociceptive axons, has demonstrated reliability equivalent to nerve conduction velocity⁶⁹, and age and gender specific normative data are available⁵². Epidermal axons are capable of regeneration in surgical and chemical axotomy models^{70,71}, and small studies suggest IENFD improves following intervention for diabetic neuropathy¹¹ and idiopathic neuropathy in the setting of prediabetes¹⁰. A small open label trial of topiramate in diabetic neuropathy demonstrated improved IENFD and microvascular reactivity²⁵ and a small randomized trial of topiramate versus ruboxistaurin or placebo demonstrated improvement in IENFD and the Total Neuropathy Score⁷² among the topiramate treated participants²⁴.

10.1.2. Secondary Outcome(s)

Secondary outcome measures will include measures of neuropathy symptoms and signs, function and mobility, nerve conduction studies, and metabolic assessment.

i. Neuropathy symptoms:

1. **NTSS6**⁵³

3. **Brief Pain Inventory – Diabetic Neuropathy (BPI-DN)**⁵⁴

ii. Neuropathy signs:

1. **Utah Early Neuropathy Scale**⁴⁸

iii. Function and mobility

1. **6-minute walk test (6MWT)**⁵⁶

2. **Timed up and Go (TUG)**⁵⁸

3. ABC Scale.

iv. Nerve conduction studies including Sural sensory amplitude and distal latency/conduction velocity, and Peroneal motor amplitude, distal latency, conduction velocity between the knee and ankle as described above.

v. Metabolic assessment:

- Height, weight, BMI, waist circumference
- Fasting glucose and insulin with calculation of the “quantitative insulin sensitivity check index” (QUICKI)⁷³
- Hemoglobin A1c
- Fasting lipid panel

10.1.3. Exploratory Outcomes

Mechanistic Studies: This study is not designed to conclusively elucidate the precise mechanisms underlying topiramate's potential efficacy for CSPN (weight loss and resultant metabolic improvement, Na channel inhibition), but will include biomarkers specific to these putative mechanisms. DNA will be banked from subjects who agree to the optional DNA sample collection. Once blind has been broken, the genes for voltage gated sodium channels of greatest relevance to peripheral nerve function (SCN2A, 3A, 4A, 8A, 9A and 10A) will be sequenced in subsets of subjects with the greatest and least clinical improvement in order to examine for sequence variants associated with topiramate responsiveness. The relationship between baseline weight and metabolic parameters, and their improvement, and response to therapy will also be explored. Insulin sensitivity will be assessed using an indirect surrogate index (e.g. the QUICKI)⁷³.

10.2. Data Monitoring

All aspects of the study will be monitored by qualified individuals designated by the sponsor. Monitoring will be conducted according to Good Clinical Practice and applicable government regulations. The investigator agrees to allow monitors access to the clinical supplies, dispensing and storage areas, and to the clinical files of the study subjects, and, if requested, agrees to assist the monitors.

Safety monitoring will include careful assessment and appropriate reporting of adverse events. Medical monitoring will include contemporaneous assessment of serious adverse events.

The monitoring of subject safety and data quality will follow the NINDS Guidelines for Data and Safety Monitoring in Clinical Trials. A Data and Safety Monitoring Board (DSMB) appointed by the NIH/NINDS will meet at 24-week intervals (or as determined by the NINDS) to review partially unblinded study data provided by the study statistician. This committee will monitor rates of adverse events and endpoints in the trial and will monitor the performance of the trial. The frequency and format of DSMB meetings, reports, and guidelines for interim analysis will be agreed upon prior to study subject enrollment.

The Protocol PI will appoint an Independent Medical Monitor (IMM) to review all adverse events, in a blinded fashion, on a periodic basis. In addition, the IMM will review all events that meet the regulatory definition of a Serious Adverse Event, upon receipt of notification via the Electronic Data Capture (EDC) system.

An adverse event (AE) is any unfavorable and unintended sign (including a clinically significant abnormal laboratory finding, for example), symptom, or disease temporally associated with a study, use of a drug product or device whether or not considered related to the drug product or device. The FDA, Office of Human Research Protection (OHRP), and NeuroNEXT CIRB requirements for reporting AEs will be followed. Subjects will be monitored for AEs from the time they sign consent until 30 days following permanent discontinuation of study drug. Adverse events during the screening phase (from the time the subject signs consent until they are randomized) shall only include events related to study procedures, i.e. infection of skin biopsy site.

At that point, all ongoing AEs will be followed to resolution, but no new AEs will be recorded. The IMM/DSMB will review cumulative AEs; the frequency of this review will be determined by the IMM/DSMB in conjunction with the Protocol PI.

Each Clinical Study Site Investigator and research team (co-Investigators, research nurse, clinical trial coordinator) are responsible for identifying and reporting AEs and determining the relationship of the event to the study drug/study procedures. Aggregate reports blinded by treatment group, detailed by severity, attribution (expected or unexpected), and relationship to the study drug/study procedures, will be available from the DCC for review by the IMM. A separate report detailing protocol compliance will also be available monthly from the DCC for review by the Protocol PI, who will provide feedback to individual sites as needed. The Protocol Steering Committee (PSC) will advise the Protocol PI as to whether the protocol or informed consent document requires revision based on these reports.

